13.3 Procedures for Termination or Suspension

13.3.1 *Medtronic-initiated and Regulatory Authority-initiated*

- Medtronic will promptly inform the clinical investigators of the termination or suspension and the reasons and inform the regulatory authority(ies) where required
- In the case of study termination or suspension for reasons other than a temporary IRB approval lapse, the investigator will promptly inform the IRB.
- In the case of study termination, the investigator must inform the subjects and may inform the personal physician of the subjects to ensure appropriate care and follow-up is provided
- In the case of a study suspension, subject enrollment must stop until the suspension is lifted by Medtronic
- In the case of a study suspension, enrolled subjects should continue to be followed out of consideration of their safety, rights and welfare

13.3.2 *Investigator-initiated*

- The investigator will inform Medtronic and provide a detailed written explanation of the termination or suspension
- The investigator will promptly inform the institution (where required per regulatory requirements)
- The investigator will promptly inform the IRB
- The investigator will promptly inform the subjects and/or the personal physician of the subjects to ensure appropriate care and follow-up is provided
- In the case of a study suspension, subjects enrolled should continue to be followed out of consideration of their safety, rights and welfare

13.3.3 *IRB-initiated*

- The investigator will inform Medtronic and provide a detailed written explanation of the termination or suspension within 5 business days
- Subject enrollment must stop until the suspension is lifted
- Subjects already enrolled should continue to be followed in accordance with IRB policy or its determination that an overriding safety concern or ethical issue is involved
- The investigator will inform his/her institution (where required per local requirements)
- The investigator will promptly inform the subjects, or legally-authorized designees and/or the personal physician of the subjects, with the rationale for the study termination or suspension.

14 STATISTICAL METHODS AND DATA ANALYSIS

14.1 General Considerations

Medtronic statisticians or designee will conduct all statistical analyses. The study is an event driven study with no formal statistical hypothesis planned. A separate Statistical Analysis Plan (SAP) will be developed and include a comprehensive description of the statistical methods and reports to be included in the final study report. Any change to the data analysis methods described in the protocol will require an amendment only if it changes a principal feature of the protocol. Any other change to the data analysis methods described in the protocol, and the justification for making the change, will be described in the clinical study report.

14.2 Primary Objective

The primary objective is to characterize Reveal LINQ™ derived data from patients with heart failure by assessing the relationship between changes in LINQ™ derived data and other physiologic parameters with subsequent ADHF events.

14.2.1 Endpoint Definitions

why is the descriptive statistics redacted? (BN)

The ADHF events as adjudicated by the CEC that will be used in the primary analysis are those that are ≥ 30 days following implant in order to ensure sufficient LINQ™ derived data prior to the event onset are available. A second ADHF event within a subject may be used if the second ADHF event is > 90 days following the first event. In the event a subject has > 2 qualifying ADHF events, only the first two will be used in the primary analysis. Additional analyses including all qualifying ADHF events may be conducted.

14.2.2 Analysis Methods

Physiologic data (including heart rate, bioimpedance, activity, blood pressure and weight), as well as blood samples (including serum BUN, creatinine, NT-proBNP, hemoglobin, hematocrit, troponin, eGFR and electrolytes), will be collected from subjects with acute decompensated heart failure.

[REDACTED] Data will be collected from enrollment up to 3 years post-insertion. If a subject exits the study prematurely, data captured prior to exit will be included in the analysis. All data collected will be included in the analysis. Descriptive statistics (e.g. means, standard deviations, proportions) will be used to summarize the physiological and derived data recorded. Analyses will be conducted to assess changes in the physiologic and LINQ™ derived data in association with HF events.

14.2.3 Determination of Patients/Data for Analysis

All subjects with a successful insertion will be used in the analysis.

14.2.4 Sample Size

There are no sample size requirements as this is an observational study. The sample size was selected in order that data can be derived from an estimated 40 subjects with a

HF event within 12 months. This provides a conservative estimate of the required number of subjects. The CHAMPION study provides a 12 month KM estimate of HF hospitalization of 30% for Class III subjects.¹⁷ To be conservative, it is assumed 25% of enrolled subjects will have at least one HF event within 12 months. If the estimate is used as a binomial proportion, a sample size of 300 subjects would accrue ≥ 40 subjects with event within 12 months with $> 99\%$ probability. If the proportion of subjects with HF event is lower than 25%, the probability of at least 40 subjects with at least one HF event is $> 91\%$ if the underlying proportion of subjects with event is $\geq 16\%$. The projected enrollment number of 300 may be readjusted if the frequency of HF events is higher or lower than anticipated.

14.2.5 Heart Failure (HF) Event Definition

A heart failure event is defined as any cardiovascular-related (including hypervolemia) Health Care Utilizations (HCUs) for any one of the following events.

- Admission with primary diagnosis of HF
- Intravenous HF therapy (e.g. IV diuretics/vasodilators) or ultrafiltration at any one of the following settings:
 - Admission with secondary/tertiary diagnosis of HF
 - Emergency Department
 - Ambulance
 - Observation Unit
 - Urgent Care
 - HF/Cardiology Clinic

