7.3.2 Exclusion criteria

- Patient is pregnant (all females of child-bearing potential must have a negative pregnancy test within 1 week of enrollment)
- Patient is enrolled in another study that could confound the results of this study, without documented pre-approval from a Medtronic study manager
- Patient has severe valvular heart disease as defined by hemodynamically significant valve stenosis and/or prosthetic heart valve
- Patient has existing IPG, ICD, CRT-D or CRT-P device
- Patient has severe renal impairment (eGFR <25mL/min)

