
Serious Adverse Event (SAE) (ISO 14155:2011, 3.37)
	
Adverse event that a) led to death, b) led to serious deterioration in the health of the subject, that either resulted in 1) a life-threatening illness or injury, or 2) a permanent impairment of a body structure or a body function, or 3) in-patient or prolonged hospitalization, or 4) medical or surgical intervention to prevent life-threatening illness or injury or permanent impairment to a body structure or a body function, c) led to foetal distress, foetal death or a congenital abnormality or birth defect
 
NOTE 1: Planned hospitalization for a pre-existing condition, or a procedure required by the CIP, without serious deterioration in health, is not considered a serious adverse event.

Serious Adverse Device Effect (SADE) (ISO 14155:2011, 3.36)
	
Adverse device effect that has resulted in any of the consequences characteristic of a serious adverse event.

Complication
	
An adverse event that includes the following is considered a complication:  Results in death,  Involves any termination of significant device function, or  Requires an invasive intervention
 
(21 CFR 812) Non-invasive: when applied to a diagnostic device or procedure, means one that does not by design or intention:  Penetrate or pierce the skin or mucous membranes of the body, the ocular cavity, or the urethra, or  Enter the ear beyond the external auditory canal, the nose beyond the nares, the mouth beyond the pharynx, the anal canal beyond the rectum, or the vagina beyond the cervical os.
 
For purposes of this part, blood sampling that involves simple venipuncture is considered noninvasive, and the use of surplus samples of body fluids or tissues that are left over from samples taken for non-investigational purposes is also considered noninvasive.

Observation
	
Any adverse event that is not a complication.

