11.6 Clinical Events Committee (CEC) review

At regular intervals, an independent Clinical Events Committee (CEC) will conduct a medical review of AEs, HCU and deaths for subjects participating in the study.

The CEC will consist of a minimum of three (3) non-Medtronic employed physicians that are not participating investigators for the study, including a CEC chairperson. At a minimum, the CEC will adjudicate all adverse events, deaths, and HCU as defined in section 14.2.5.

Medtronic personnel may facilitate and participate in a CEC meeting but will be non-voting members.

For adverse events and deaths reviewed by the CEC, Medtronic will provide the CEC with the Investigator's description and classification. The CEC is responsible for reviewing the Investigator's assessment and supportive documentation (when available), reviewing applicable definitions, and determining final classifications for all adjudication parameters. For adverse events, classification includes relatedness and complication or observation. Additionally, the CEC will provide an adjudication of the death classification for all reported deaths including primary cause of death, relatedness, and cardiac classification.

If the CEC disagrees with the investigator's classification of the event, the rationale will be provided to the investigator. If the investigator agrees with the CEC's adjudication, the case report form documenting the AE will be updated accordingly.

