7.9.2. Performance Requirements

Performance requirements are not pre-specified for this objective. The ADHF events as adjudicated by the CEC that will be used in the primary analysis are those that are ≥ 30 days following implant in order to ensure sufficient LINQ™ derived data prior to the event onset are available. A second ADHF event within a subject may be used if the second ADHF event is > 90 days following the first event. In the event a subject has > 2 qualifying ADHF events, only the first two will be used in the primary analysis. Additional analyses including all qualifying ADHF events may be conducted.

A heart failure event is defined as any cardiovascular-related (including hypervolemia) Health Care Utilizations (HCUs) for any one of the following events.

- Admission with primary diagnosis of HF
- Intravenous HF therapy (e.g. IV diuretics/vasodilators) or ultrafiltration at any one of the following settings:
 - Admission with secondary/tertiary diagnosis of HF
 - Emergency Department
 - Ambulance
 - Observation Unit
 - Urgent Care
 - HF/Cardiology Clinic

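### The ADHF endpoint has no acute, worsening or unplanned criterion, so a planned HF admission can qualify and enter the pre-event average

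*Combined protocol and SAP*

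**What the plan says.** The only event definition is in protocol 14.2.5, and SAP 7.9.2 repeats it. The stem reads "A heart failure event is defined as any cardiovascular-related (including hypervolemia) Health Care Utilizations (HCUs) for any one of the following events". Two limbs follow. The first is met by "Admission with primary diagnosis of HF" and nothing more. The second is met by "Intravenous HF therapy (e.g. IV diuretics/vasodilators) or ultrafiltration at any one of the following settings", and the settings listed include the HF or cardiology clinic.

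ADHF is spelled out as an abbreviation but never given criteria of its own. The two terms are used for the same target: protocol 3.2 aims for about 40 heart failure events, SAP 5 for about 40 ADHF events.

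For the primary analysis, protocol 14.2.1 says: "The ADHF events as adjudicated by the CEC that will be used in the primary analysis are those that are ≥ 30 days following implant". On the committee's remit, protocol 11.6 says that "the CEC will adjudicate all adverse events, deaths, and HCU as defined in section 14.2.5".

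Protocol 8.14 lists which healthcare utilizations (HCUs) are collected. A scheduled clinic visit is collected only if the subject has cardiovascular symptoms. Inpatient hospitalizations carry no unplanned qualifier, and hospital outpatient clinic visits carry no symptom qualifier.

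Elsewhere the protocol does make the distinction. Table 10, Note 1 removes from serious adverse events "Planned hospitalization for a pre-existing condition, or a procedure required by the CIP, without serious deterioration in health".

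**The concern.** The study asks whether device data change before decompensation. SAP 7.9.4 answers by averaging daily values across subjects for at least 14 days on each side of the first event. A contact booked in advance for a stable subject is not a decompensation and would be expected to show little change beforehand.

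Such contacts are foreseeable. Entry requires NYHA class III, and 7.3.2 excludes anyone for whom "Patient has existing IPG, ICD, CRT-D or CRT-P device". Some subjects may therefore be admitted electively during follow-up for a device implant or an evaluation, with HF as the primary diagnosis. Receiving a device is not among the exit reasons in 8.16.

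If such an admission is taken as the subject's first event:

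- It supplies day 0 and the run-up for that subject in the 7.9.4 average.
- A later genuine event is not the first event, so it drops out of that average. If it falls within 90 days, it cannot be used as the second event either.
- It counts towards the 40 events after which SAP 7.8 allows follow-up to end.
- The subject leaves the no-event reference group.

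**Working it through.** **Step 1. Is there an acuity condition anywhere between the contact and the analysis?**

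| Stage | Source | Condition on acuity |
|---|---|---|
| HCU collected: inpatient stay | Protocol 8.14 | None |
| HCU collected: hospital outpatient clinic | Protocol 8.14 | None |
| HCU collected: scheduled clinic visit | Protocol 8.14 | CV symptoms present |
| HF event | Protocol 14.2.5, SAP 7.9.2 | None |
| CEC adjudication of HCUs | Protocol 11.6 | Refers to 14.2.5 |
| Use in the primary analysis | Protocol 14.2.1 and 14.4, SAP 7.4 | Timing and device data only |

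A planned admission with HF as primary diagnosis passes every written condition. Scheduled IV therapy passes at a hospital outpatient clinic visit that falls within a listed setting, or at a scheduled clinic visit with symptoms. It does not pass at a scheduled clinic visit without symptoms.

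**Step 2. Dilution of the first-event average.** Let n be the number of subjects with a first event, k of them with a planned first event, and D the true mean change before genuine events. If planned events show no change, the observed mean is D × (n − k)/n, so the attenuation is k/n. With at most two events per subject, 40 events come from 40/2 = 20 to 40 subjects. The documents do not give k; the values below are assumptions.

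| k | n = 40 | n = 20 |
|---|---|---|
| 2 | 5% | 10% |
| 4 | 10% | 20% |
| 6 | 15% | 30% |

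If planned events show a mean change c rather than zero, the attenuation becomes (k/n) × (1 − c/D). Protocol 4 says about 90% of certain HF hospitalizations are both unplanned and potentially preventable. The remaining 10% need not be planned, and the statement concerns a different population, so it does not supply k.

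**Step 3. What an acuity rule would cost in accrual.** Take X ~ Binomial(300, p) and compute P(X ≥ 40), the 12-month chance of at least 40 subjects with an event. The protocol's own figures (14.2.4) reproduce: p = 0.25 gives 0.9999998 (stated as above 99%), and p = 0.16 gives 0.9122 (stated as above 91%). SAP 6 prints above 88% for the 16% case. That matches P(X ≥ 41) = 0.8828 and is still true as a lower bound.

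Now let a share f of events be excluded and let the subject-level rate fall in proportion, to p × (1 − f):

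| f | From 25% | P(X ≥ 40) | From 16% | P(X ≥ 40) |
|---|---|---|---|---|
| 5% | 0.2375 | >0.999 | 0.152 | 0.837 |
| 10% | 0.225 | >0.999 | 0.144 | 0.724 |
| 20% | 0.200 | 0.999 | 0.128 | 0.417 |
| 30% | 0.175 | 0.979 | 0.112 | 0.141 |

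These overstate the loss. A subject whose planned contact is excluded may still have a genuine event, follow-up runs to 3 years, and second events count towards the 40.

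**The case against.** **The CEC may already screen these contacts out.** The primary analysis uses events adjudicated as ADHF by independent physicians, and the reference in 11.6 to 14.2.5 can be read as saying which HCUs go to the committee, not how acuity is assessed. The summary of changes describes that edit as a clarification of scope. This stands to the extent that planned contacts *can* qualify, not that they automatically do. It does not close the gap, because no written criterion tells the committee to exclude them.

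**Most pre-booked infusions are not at issue.** A reader might infer from the second limb that any scheduled clinic infusion becomes an ADHF event. Protocol 8.14 does not support that: a scheduled clinic visit without cardiovascular symptoms is not a collected HCU. The remaining route is narrower, although a symptom condition is a weak filter in NYHA class III.

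**A flat run-up is an inference.** Work-up of a class III patient, or IV diuretic given for congestion, may follow real deterioration. This stands, and it is why the dilution is conditional.

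**The contrast with the serious adverse event rule is limited.** Note 1 sits in a definition attributed to ISO 14155, so it does not show that the sponsor considered planned events for the endpoint and left them in.

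**Nothing is tested.** SAP 7.9.1 to 7.9.3 set no hypothesis or performance requirement, so no decision threshold turns on the attenuation. That limits the consequence, but the averaged run-up is still the main product of the study.

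**Conclusion.** The gap is real for planned admissions with HF as primary diagnosis and for part of scheduled IV therapy. The endpoint is named for acute decompensation, while its written definition has no acute, worsening or unplanned element and CEC adjudication of HCUs is tied to that definition.

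The size is k/n with n between 20 and 40, and k is unknown. The 5% to 30% in the working rests on an assumed 2 to 6 planned first events with no mean change beforehand. A reader might instead divide by the 40 counted events. That is not the denominator of the SAP 7.9.4 average, which takes one first event per subject; a planned second event does not enter it, though it still counts towards the 40. Nor do the documents show that planned contacts will be counted in practice, only that the text permits it.

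The definition should be corrected. No figure stated in the plan is shown to be wrong by this point.

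**What to change.** In protocol 14.2.5, SAP 7.9.2 and the CEC's criteria:

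- Require that an ADHF event used in the primary analysis be unplanned, or be for new or worsening signs or symptoms of HF in the CEC's assessment.
- State that elective admissions without worsening (for a procedure, device implant or evaluation, for example) do not count.
- Have the CEC record planned or unplanned status for each adjudicated HF contact. The case report forms are under separate cover, so part of this may already be captured; the SAP 7.11 table splits clinic visits into scheduled and unscheduled but does not split admissions.

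In SAP 7.9.4, show the run-up averages with and without planned contacts.

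The cost is a short addition to each document, one item recorded at adjudication, and somewhat fewer counted events. At the assumed 25% rate the accrual cost is small even if 30% are excluded. At the 16% rate it is not negligible, as the last table in the working shows, so the event count should be tracked under the new rule.

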7.3.1 Inclusion criteria

- Patient is 18 years of age or older
- Patient (or patient's legally authorized representative) is willing and able to provide written informed consent
- Patient is willing and able to comply with the protocol, including follow-up visits and Carelink transmissions
- Patient has NYHA Class III, per most recent assessment or at any time within 30 days prior to enrollment
- Patient had a HF event (HF event defined as meeting any one of the following three criteria):
 1. Admission with primary diagnosis of HF within the last **6 months**, OR
 2. Intravenous HF therapy (e.g. IV diuretics/vasodilators) or ultrafiltration at any one of the following settings within the last **6 months**:
 - Admission with secondary/tertiary diagnosis of HF
 - Emergency Department

- Ambulance
- Observation Unit
- Urgent Care
- HF/Cardiology Clinic
- Patient's Home, OR

3. Patient had the following BNP/NTpro-BNP within the last **3 months**:

- If EF \geq 50%, then BNP > 200 pg/ml or NTpro-BNP > 400 pg/ml OR
- If EF is <50%, then BNP > 400 pg/ml or NTpro-BNP > 800 pg/ml

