8.14 Healthcare Utilization

Cardiovascular-related Health Care Utilizations (HCUs) (including hypervolemia and hypovolemia) will be collected. This includes the following:

- Unscheduled clinic visit (including subject-initiated phone calls if the subject is experiencing CV-related symptoms)
- Scheduled clinic visit (if the subject is experiencing CV-related symptoms)
- Hospital outpatient clinic visit
- Urgent care visit
- Other outpatient utilization with overnight stay
- Emergency department visit
- Inpatient hospitalization

HCU information should be reported upon center awareness and assessed at all visits including the monthly telephone visits. If multiple HCUs occur within the same day, data from all HCUs can be captured on one eCRF.

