8.17 Medications

Cardiovascular medications will be collected at the baseline assessment, 1 Month, 6 Month, 12 Month office visits and Study Exit. The name, dose, frequency and route of all cardiovascular medications will be collected. Changes to medications will be captured at healthcare utilizations.

There are no medications that are required for this study although some medications may be administered in treating specific conditions at the discretion of the physician. The only medications that are excluded from use during this study are investigational.

8.18 6 Minute Hall Walk Test

Subjects will be asked to perform a 6 Minute Hall Walk test at the 1 Month, 6 Month and 12 Month office visits. A Holter will be recommended to be worn during the 6 Minute hall walk at the 6 Month Visit only. In addition, the subjects will be asked to press the Patient Assistant device to mark the beginning and end of their 6 Minute Hall Walk test ONLY when the DR220 Holter is not used. Refer to Appendix C for more details.

[REDACTED]

[REDACTED]

[REDACTED]

[REDACTED]

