7.2. General Methodology

Data analysis will be performed by a Medtronic statistician or designee, and will be performed once at least 40 ADHF events (as adjudicated by the CEC) occurring at least 30 days post-Reveal LINQ implant have been obtained from subjects who received the downloaded RAMware and have data for the most recent 30 days prior to the event. No more than two events per subject will be included in the analysis, and those two events must be at least 90 days apart.

All analyses will be performed on an "As Treated" basis.

The cohort will include all enrolled subjects who received the downloaded investigational LINQ HF RAMware and experienced ADHF events at least 30 days post-implant. Subjects who do not experience ADHF events may also be included as a reference dataset for baseline readings of measurements (i.e. profile of measurements that do not precede ADHF events).

Any tests of treatment effects will be conducted at a two-sided alpha level of 0.05 unless otherwise stated.

Any change to the data analysis methods described in the protocol will require an amendment only if it changes a principal feature of the protocol. Any other change to the data analysis methods described in the protocol, and the justification for making the change, will be described in the clinical study report.

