7.9.4. Analysis Methods

Physiologic data (including heart rate, bioimpedance, activity, blood pressure and weight), as well as blood samples (including serum BUN, creatinine, NT-proBNP, hemoglobin, hematocrit, troponin, eGFR and electrolytes), will be collected from subjects with acute decompensated heart failure. [REDACTED]

This document is electronically controlled. Printed copies are considered uncontrolled.

Confidential

The following table lists out the RAMware features and frequency of measurements.

[REDACTED]	[REDACTED]	[REDACTED]
[REDACTED]	[REDACTED]	[REDACTED]
[REDACTED]	[REDACTED]	[REDACTED]
	[REDACTED]	[REDACTED]
	[REDACTED]	[REDACTED]
[REDACTED]	[REDACTED]	[REDACTED]
	[REDACTED]	[REDACTED]
[REDACTED]	[REDACTED]	[REDACTED]

[figure not shown]
Data will be collected from enrollment up to 3 years post-insertion. If a subject exits the study prematurely, data captured prior to exit will be included in the analysis. All data collected will be included in the analysis. Descriptive statistics (e.g. means, standard deviations, proportions) will be used to summarize the physiological and derived data recorded. Analyses will be conducted to assess changes in the physiologic and LINQ™ derived data in association with HF events.

For each subject whose device contains the downloaded RAMware, the measurements in the table above will be averaged to produce one mean value for each feature for each day. Then for subjects who experience at least one ADHF event, the daily mean values will be averaged across subjects for each day leading up to the first event per subject and each day following that event for a minimum of 14 days on either side of admission. For example, if 40 subjects have at least one ADHF event, then for each of the 14 days prior to that event, the 40 subjects' mean values for that day will be averaged. The same will be done for the 14 days following ADHF admission. This will be done for each of the features above.

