7.11. Health Outcomes Analyses

Healthcare utilizations will be adjudicated by the CEC. A summary table will be generated showing the prevalence of each HCU type. The format of the table will be as presented below. All HCUs will be included in the table below. Because multiple HCU's occurring on the same day will be recorded on one HCU form, only the most severe HCU type (using the hierarchy in the table below) will be taken for each form. For example, if a subject presented at the Emergency Department and then is admitted to an inpatient hospitalization, that HCU will be considered an inpatient hospitalization for purposes of analysis.

Healthcare Utilization Type	Number of HCUs (Number, % of Subjects With HCU)	
	All HCUs	HF-related HCUs
Inpatient Hospitalization	X (Y, %)	X (Y, %)
Emergency Department Visit	X (Y, %)	X (Y, %)
Hospital Outpatient Clinic Visit	X (Y, %)	X (Y, %)
Other Outpatient Utilization with overnight stay	X (Y, %)	X (Y, %)
Urgent Care visit	X (Y, %)	X (Y, %)
Clinic Visit	X (Y, %)	X (Y, %)
Scheduled	X (Y, %)	X (Y, %)
Unscheduled	X (Y, %)	X (Y, %)
Phone Call	X (Y, %)	X (Y, %)
Total Events	X (Y, %)	X (Y, %)

Additionally, the monthly rate of heart failure-related HCUs will be determined, allowing for multiple events per subject. The monthly rates will be calculated for each month post-insertion. For each month (e.g. 0-30 days, 31-61 days, etc.), the number of HF-related HCUs occurring in that interval will be divided by the total number of follow-up months for that interval (each subject can contribute a minimum

This document is electronically controlled. Printed copies are considered uncontrolled.

Confidential

of 0 months and a maximum of 1 month for each interval). The intervals for month K ($K=1,2,\dots,30$) will be determined by multiplying 30.44 days by K-1 and K and rounding each to the nearest whole number. As described above, if multiple HCU types are recorded on one HCU form, this will count as one total HCU.

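### Should intravenous heart-failure therapy at home, which counts as an HF event at entry, also count as an event during follow-up?

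*Combined protocol and SAP*

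**What the plan says.** The inclusion criteria (protocol synopsis, protocol 7.3.1, SAP 5) accept intravenous HF therapy or ultrafiltration in the previous 6 months in seven settings, ending with "Patient's Home, OR". Qualifying BNP or NT-proBNP values are a further route.

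The follow-up definition is worded alike in protocol 14.2.5 and SAP 7.9.2. It opens "A heart failure event is defined as any cardiovascular-related (including hypervolemia) Health Care Utilizations (HCUs) for any one of the following events" and then gives two routes: admission with HF as primary diagnosis, or "Intravenous HF therapy (e.g. IV diuretics/vasodilators) or ultrafiltration at any one of the following settings". Six settings follow. Home is not among them.

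Protocol 8.14 lists the types of healthcare utilization (HCU) collected. One is "Unscheduled clinic visit (including subject-initiated phone calls if the subject is experiencing CV-related symptoms". There is no home-treatment type. Protocol 8.17 adds "Changes to medications will be captured at healthcare utilizations". SAP 7.11 says "Healthcare utilizations will be adjudicated by the CEC", while protocol 11.6 sets the minimum HCU scope of the Clinical Events Committee (CEC) by reference to 14.2.5.

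SAP 7.9.4 averages daily device values around each subject's first event "for a minimum of 14 days on either side of admission". Subjects without an included event supply the comparison curve, and SAP 7.2 describes such reference data as a "profile of measurements that do not precede ADHF events".

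**The concern.** The two lists share their lead-in wording and their first six settings in the same order, and the follow-up list stops one item short. That looks like a dropped line. If home therapy shows a decompensation serious enough to qualify a patient, one would expect it to count after insertion too.

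Two consequences would follow. A subject whose only treated episode was at home has no ADHF event, so the days around that episode are averaged into the reference curve, which is meant to show readings away from decompensation. If a counted event follows soon after home treatment, the home episode lies unflagged in the pre-event days. Either could blur the contrast between pre-event and reference profiles. Fewer countable episodes could also slow the path to 40 events.

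**Working it through.** **1. The lists side by side**

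| Route or setting | Entry | Follow-up |
|---|---|---|
| Admission, HF primary diagnosis | yes | yes |
| IV therapy: admission with HF as secondary or tertiary diagnosis | yes | yes |
| IV therapy: emergency department | yes | yes |
| IV therapy: ambulance | yes | yes |
| IV therapy: observation unit | yes | yes |
| IV therapy: urgent care | yes | yes |
| IV therapy: HF or cardiology clinic | yes | yes |
| IV therapy: patient's home | yes | no |
| BNP or NT-proBNP threshold | yes | no |

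Home is the only setting dropped, but not the only entry route dropped. The entry list selects patients at raised risk. The follow-up list picks dated encounters that a committee can adjudicate and on which daily profiles can be aligned. The follow-up column is the same in protocol and SAP, so the outcome is not in doubt.

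**2. Link to data collection.** A follow-up event must be an HCU. The types in protocol 8.14 are clinic, hospital outpatient, urgent care, overnight outpatient, emergency and inpatient encounters. Home fits none of them. The match is imperfect, because ambulance is not named there either, but leaving out home agrees with what is collected.

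**3. Event accrual.** The plan's own figures first: with X ~ Binomial(300, p), P(X ≥ 40) = 0.9999998 at p = 0.25 (stated > 99%) and 0.912 at p = 0.16 (protocol states > 91%; SAP states > 88%). The 25% was set below a 30% twelve-month rate of HF hospitalization, so no home-treated events were built into it. Even if 20% of event subjects were lost as home-only (an assumption), p = 0.25 × 0.80 = 0.20 and P(X ≥ 40) = 0.999. If the 16% scenario is read as including home-only subjects, the same kind of loss matters more: 0.886 at 2% lost, 0.724 at 10%. But these probabilities count subjects within 12 months, whereas the operating target is 40 events, with up to two per subject and follow-up of up to 3 years.

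**4. Reference curve.** Inputs from the plan: 300 subjects, 25% with an event, 14 days either side. Assumption: 3 to 15 subjects (1 to 5%) have one home-only episode.

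- Reference subjects: 300 × 0.75 = 225. Subject-days in one year: 225 × 365 = 82,125.
- Affected window: 14 + 1 + 14 = 29 days.
- All assumed subjects in the reference: 3 × 29 = 87 days, 87 / 82,125 = 0.11%; 15 × 29 = 435 days, 435 / 82,125 = 0.53%.
- Only a proportional 75% in the reference: 2.25 × 29 = 65.25 days (0.08%); 11.25 × 29 = 326.25 days (0.40%).

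If affected days differ from other days by d on some feature, the reference mean moves by the affected fraction times d, so by at most 0.0053 × d.

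**5. Pre-event profile.** One overlapping window among 40 first events has weight 1/40 = 2.5%. That is a weight, not a bias, and the number of overlaps is unknown.

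**The case for a change.** The strongest case for acting is that the plan nowhere says the omission is deliberate, and the HCU explanation does not settle it, since ambulance is absent from protocol 8.14 yet kept in the follow-up list. The data are meant to generate hypotheses about prediction, so a clean reference has value, and one sentence per document would cost little. All of this is true. What stands is a missing rationale.

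The analytic part is weaker:

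- By SAP 7.2's own terms the reference holds readings that do not precede ADHF events. A home-only episode is not an ADHF event under SAP 7.9.2, so the SAP does not breach its own description.
- Home is not a special case. SAP 7.9.4 places in the reference every subject without an included event. That also covers subjects whose only adjudicated event came before day 30 or lacked 30 days of device data (SAP 7.4, 7.9.2). Removing home episodes alone would leave these full ADHF events in place.
- Home treatment shortly before a counted admission may be part of the same worsening, which is the lead-up the study sets out to describe. Dropping such windows is a preference.
- It is not shown that home infusions would be identifiable. Protocol 8.14 collects calls and visits, not infusions, and the committee's minimum scope refers back to a definition without home. The case report forms are under separate cover.
- Adding home to the event list is a trade-off: source documents for adjudication may be thinner, and an admission within 90 days of a home event could no longer serve as a second event.

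**Conclusion.** The discrepancy is real but calls for no change. Protocol and SAP agree on the follow-up definition, an eligibility criterion need not equal an outcome definition, and the omission fits the HCU types collected. What is missing is a reason, and an analyst can apply the definition without it.

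Under the assumed 1 to 5% of subjects with one home-only episode, the reference curve is touched on about 0.1 to 0.5% of subject-days over one year. That would not alter descriptive profiles in a study with no hypothesis or performance requirement. The frequency of home therapy is not in the documents, so this range is an illustration; a much higher frequency would raise it in proportion. Event accrual is safe at the 25% planning rate.

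Anyone wanting a purer reference should look at the general SAP 7.9.4 rule on subjects without an included event, not at this one setting.
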